A phase 1, single-center, double-blind, placebo-controlled clinical study to evaluate the safety, tolerability, and pharmacokinetics of TNP-2092 Capsules, and the food effect on the pharmacokinetics of TNP-2092 Capsules after single-dose oral administration in healthy subjects.

Protocol

Protocol No.: TNP-2092-01

Approval Date: 19 May 2016

ClinicalTrials.gov ID: NCT06178718

Protocol Synopsis of Study TNP-2092-01

Name of Sponsor Company: TenNor Therapeutics (Suzhou) Limited.	Individual Study Table Referring to Part of the Dossier	(For National Authority Use Only)
Name of Finished Product: TNP-2092 capsules	Volume: Page:	
Name of Active Ingredient: TNP-2092		
Title of study: A phase 1, single-center, double-blind, placebo-controlled clinical study to evaluate the safety, tolerability, and pharmacokinetics of TNP-2092 Capsules, and the food effect on the pharmacokinetics of TNP-2092 Capsules after single-dose oral administration in healthy subjects		
Investigator: [name], The First Hospital of Jilin University		
Study center: A single center.		
Clinical Phase: 1		
Objectives 1) To evaluate the safety and tolerability of TNP-2092 Capsules in healthy subjects after single-dose escalated oral administration. 2) To evaluate the pharmacokinetic characteristics of TNP-2092 Capsules. 3) To evaluate the effect of eating on the pharmacokinetics of TNP-2092 Capsules after single-dose oral administration in healthy subjects.		
Methodology This is a single-center, randomized, double-blind, placebo-controlled, dose-ascending single-dose-administration study, and a study on the food effects on pharmacokinetics. Five dose groups of 100 mg, 200 mg, 400 mg, 800 mg, and 1200 mg will be set up. The 100 mg, 200 mg, 800 mg, and 1200 mg groups will complete the single administration clinical study, with 10 subjects randomized in each group, 8 subjects receiving TNP-2092 and 2 receiving placebo. The drug will be administered once in each group in the fasting state, and tolerability will be evaluated on D4. Subjects were sequentially enrolled into different dose groups in ascending order of dose, and only when the previous lower dose was confirmed to be safe and well tolerated could they be enrolled into the next higher dose group. The 400 mg group will complete the clinical study on single administration and the effects of eating on pharmacokinetics and undergo the metabolic transformation evaluation. A total of 18 subjects will be enrolled in the group and randomized into Group A and Group B, with 8 subjects receiving the investigational product and 1 receiving placebo. The drugs will be administered in the fasting state and in the fed state for two cycles, with a wash-out period of 4 days. In terms of the administration sequence, Group A will first take TNP-2092 Capsules or placebo in the fasting state, and then TNP-2092 Capsules or placebo in the fed state; Group B will first take TNP-2092 Capsules or placebo in the fed state, and then TNP-2092 Capsules or placebo in the fasting state. Tolerability evaluation will be conducted on D4 and at the end of the study of food effects on pharmacokinetics (D8). The study of the 400 mg group is conducted on the premise that the tolerability evaluation result of the 200 mg group is favorable. After that, if the tolerability evaluation result in the 400 mg group is favorable for the first cycle, the second-cycle clinical study of the 400 mg group and the 800 mg group could be conducted in parallel.		

Name of Sponsor Company: TenNor Therapeutics (Suzhou) Limited.	Individual Study Table Referring to Part of the Dossier Volume: Page:	(For National Authority Use Only)
Name of Finished Product: TNP-2092 capsules		
Name of Active Ingredient: TNP-2092		

During the study, blood samples will be collected from the subjects at the specified time points and used for pharmacokinetic analysis. Also, urine and stool samples will be collected from Group A in the 400 mg group in the first cycle for the metabolic transformation study.

- Plasma sample
 - 100 mg, 200 mg, 800 mg and 1200 mg dose groups: For each group, samples are collected before the first (D1) administration (within 15 minutes), and 0.5 h, 1 h, 2 h, 3 h, 4 h, 6 h, 8 h, 10 h, 12 h, 16 h, 24 h, 36 h, 48 h and 72 h after administration, with 4 mL collected at each time point.
 - 400 mg dose group
 - ◆ Day 1: Before administration (within 15 minutes), and 0.5 h, 1 h, 2 h, 3 h, 4 h, 6 h, 8 h, 10 h, 12 h, 16 h, 24 h, 36 h, 48 h and 72 h after administration.
 - ◆ Day 5: Before administration (within 15 minutes), and 0.5 h, 1 h, 2 h, 3 h, 4 h, 6 h, 8 h, 10 h, 12 h, 16 h, 24 h, 36 h, 48 h and 72 h after administration.
- Urine sample
 - Group A of the 400 mg dose group: Urine samples are collected at 0 h before administration on D1, and 0-6 h, 6-12 h, 12-24 h, 24-48 h and 48-72 h after administration.
- Stool sample
 - Group A of the 400 mg dose group: Stools are collected whenever available within 72 hours after administration on D1.

Number of subjects

It is planned to enroll 58 subjects. Ten subjects will be administrated with placebo, and 48 subjects will be administrated with TNP-2092 capsules (8 subjects each with 100 mg, 200 mg, 800 mg or 1200 mg and 16 subjects with 400 mg).

Diagnosis and main criteria for inclusion

Each subject is required to meet all of the following criteria to be eligible for study enrollment:

- 1) Adult males or females
- 2) Eighteen to 45 years of age, inclusive
- 3) BMI: 19.0-26.0 kg/m², including 19.0 and 26.0 kg/m²
- 4) Female subjects of childbearing potential must agree to abstinence or take effective contraceptive measures during the trial and at least 70 days (10 weeks) after administration
- 5) Male subjects must agree to abstinence or use condoms as a contraceptive measure during the trial and at least 70 days (10 weeks) after administration
- 6) Subjects whose clinical laboratory test results are within the normal range or abnormal tests are judged to be no clinical insignificance by the investigator
- 7) Those who do not smoke, or have smoked less than 5 cigarettes per day within 3 months before screening; those who do not drink alcohol, or have drunk less than 14 units of alcohol per week (1 unit of alcohol = 360 mL of beer or 45 mL of spirits with 40% alcohol content or 150 mL of wine) within 6 months before screening; those who have not smoked or drunk alcohol within 48 hours before admission to the study site
- 8) Those who are fully informed of and understand this study, and have signed the Informed Consent Form
- 9) Those who are willing to follow and able to complete all the trial procedures

Name of Sponsor Company: TenNor Therapeutics (Suzhou) Limited.	Individual Study Table Referring to Part of the Dossier Volume: Page:	(For National Authority Use Only)
Name of Finished Product: TNP-2092 capsules		
Name of Active Ingredient: TNP-2092		
Subjects meeting any of the following criteria are ineligible for study enrollment:		

 1) Those with symptoms or medical history of cardiovascular, digestive, respiratory, urinary, neurological, blood, immune, endocrine system diseases or tumor, mental illness, or any condition which, in the opinion of the investigator, may threaten the safety of the subjects or affect the correctness of the trial results 2) Pregnant or lactating women 3) Those whose blood pressure is above 150/90 mmHg or below 85/55 mmHg (supine position) 4) Those with regular use of any prescription/over-the-counter drugs, including vitamins, minerals, nutritional supplements, or herbs, within 2 weeks before enrollment and during the study period 5) Those who are HIV positive, syphilis positive, hepatitis B surface antigen positive, hepatitis C antibody positive, and/or with a positive drug urine test result 6) Those who have a history of alcohol or drug abuse in the past 10 years 7) Those with an allergic constitution, a history of allergic diseases or a history of drug allergy 8) Those who have had beverages or foods containing methylxanthine (coffee, tea, coke, chocolate, and energy drinks), grapefruit (fruit juice) and alcohol within 48 hours (2 days) before the clinical study 9) Those who have taken any drug that changes the activity of liver enzymes 28 days before taking the investigational product or during the study 10) Those who have donated blood within 3 months before enrollment 11) Those who have participated in any clinical trials within 3 months before enrollment 12) Those who are the staff of the study site directly affiliated to this study or are their immediate family members. Immediate family members are defined as spouses, parents, children or siblings, whether related by blood or legally adopted 13) Those who are employees of TenNor Therapeutics 14) Other circumstances deemed by the investigator to be unsuitable for the subject to participate in this study. 		
Investigational product, dose and regimen of administration 
Investigational product: TNP-2092 capsules
 
Dose and regimen of administration: the doses were 100 mg, 200 mg, 400 mg, 800 mg, and 1,200 mg. For the administration in the fasted state, subjects are required to fast overnight for at least 10 hours and to take capsule with 240 ml of warm water. For the administration in the fed state, subjects are required to fast overnight for at least 10 hours and take high-fat meal 30 min before receiving capsule with 240 mL warm water. Meals should be controlled to finish just before administration.
		
Duration of treatment Approximately up to 22 days from signing ICF to the end of the study).		
Reference treatment, dose and regimen of administration 
Placebo: TNP-2092 placebo capsules
 
Dose and regimen of administration: the same regimen as that of TNP-2092 capsules.
		
Criteria for evaluation Pharmacokinetics		

Name of Sponsor Company: TenNor Therapeutics (Suzhou) Limited.	Individual Study Table Referring to Part of the Dossier Volume: Page:	(For National Authority Use Only)
Name of Finished Product: TNP-2092 capsules		
Name of Active Ingredient: TNP-2092		

T_{max}, C_{max}, $t_{1/2}$, $AUC_{0-\infty}$, AUC_{0-t}, the amount of drug excreted in the urine at 72 hours after administration (Ae_{0-t}), the amount of drug excreted in feces at 72 hours after administration (Ae_{0-t}), the cumulative drug excretion rate in urine, the cumulative drug excretion rate in feces, and CL.
		

Safety incidence of AEs, the relationship between the drug and AEs, severity of AEs, physical examination, clinical laboratory tests (hematology, blood chemistry, coagulation and urine test), vital signs (blood pressure, pulse and body temperature) and 12-lead ECG.
		

Efficacy Not applicable.
		

Statistical methods SAS 9.4 will be used for the statistical analysis.
		

Sample size simulation This study is a early phase exploratory clinical trial, and the sample size was not based on statistical hypothesis test. Study sample size is chosen based on the assessment of safety, PK, and preliminary efficacy in line with similar trials. The sample size of 10 subjects per group, and additional 8 subjects in the 400 mg group for food effect study are also appropriate for the purpose of the exploration of the PK profile and safety of TNP-2092 capsules.
		

Population for analyses
 
 • Full Analysis Set (FAS): all the subjects who were randomized into groups. • Safety Analysis Set (SS): all the subjects who have been randomized into groups and received at least one dose of study drug. • PK Concentration Analysis Set (PKCS): all the subjects who have been randomized into groups, received at least one dose of study drug, and have at least one evaluable blood drug concentration. • PK Parameter Analysis Set (PKPS): all subjects who have been randomized into groups, have received at least one dose of study drug, and have at least one evaluable pharmacokinetic parameter. • Bioequivalence Set (BES) of food effect: All subjects with no significant protocol violations, no protocol deviations that had impact on PK endpoints (e.g., AUC, C_{max}), who must have received at least one cycle of treatment in the crossover study and have at least one evaluable pharmacokinetic parameter. 		

Interim analysis No interim analysis is planned.
		

PK analysis PK parameters will be estimated by non-compartmental method using WinNonlin 6.4. Pharmacokinetic analysis will be based on the PKPS. Pharmacokinetic concentration and parameters will be subjected to descriptive analysis by dose group. The mean and individual drug-time curves will be shown graphically. Numbers will include individual values and mean values. In addition, individual and mean dose standardization parameters will be plotted against the dose to evaluate whether there are any obvious trends.
		

Name of Sponsor Company: TenNor Therapeutics (Suzhou) Limited.	Individual Study Table Referring to Part of the Dossier Volume: Page:	(For National Authority Use Only)
Name of Finished Product: TNP-2092 capsules		
Name of Active Ingredient: TNP-2092		
Food effect analysis		

The bioequivalence evaluation principle will be used to evaluate whether food affects the bioavailability of TNP-2092 Capsules. That is, if compared with the PK parameters of TNP-2092 Capsules in the fasting state, the 90% confidence intervals of C_{max}, AUC_{0-t} and $AUC_{0-\infty}$ of TNP-2092 Capsule in the fed state are within 80.00% - 125.00% of the corresponding PK parameters, it can be considered that there is no significant difference in the main pharmacokinetic parameters between the two modes of administration, i.e., food has no effect on the pharmacokinetics of TNP-2092 Capsules. The main pharmacokinetic parameters (AUC and C_{max}) are subjected to variance analysis after log transformation, and the geometric mean ratios of AUC_{0-last}, AUC_{0-inf}, C_{max} and their 90% confidence intervals are calculated under the postprandial and fasting administration modes.
		
Safety and tolerability Analysis		

It will be based on the SS. Physical examination results and changes, laboratory test results and changes, vital signs results and changes, as well as ECG results and changes will be subjected to descriptive analysis by dose group and planned time point. The abnormal results of these examinations will also be listed. Adverse events will be coded using the Medical Dictionary for Regulatory Activities (MedDRA), and summarized by treatment group and dose according to the system organ class and preferred terms. In addition, serious adverse events and adverse events leading to dropout and death will be listed separately.
		
Efficacy analysis		
Not applicable.		

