Appendix 1 Study Procedures - 1 (100 mg, 200 mg, 800 mg, and 1200 mg groups)

Study procedures	Screening visit ¹ (Day -14 to Day -2)	100 mg, 200 mg, 800 mg and 1200 mg groups				
		Day -1	Day 1	Day 2	Day 3	Day 4
Screening						
Signing of ICF	X					
Demography	X					
Medical and surgical history	X	X				
Concomitant medications	X	X	X	X	X	X
Chest X-ray	X					
Hepatitis B and hepatitis C tests	X					
Syphilis test	X					
HIV test	X					
Alcohol and drug test	X	X				
Blood pregnancy test	X	X				X
Verification of inclusion and exclusion criteria	X	X				
Admission		X				
Randomization		X				
Tolerability Assessment						
Clinical laboratory tests (hematology, blood biochemistry, coagulation, urinalysis, and stool routine) ²	X	X ³		X (24 h)		X (72 h)
Physical examination ²	X	X				X
12-lead ECG ²	X	X	X (pre-60 min ⁴ ; post 0.5,2,4,8,12 h)	X (24 h)	X (48 h)	X (72 h)
Vital signs ²	X	X	X (pre-60 min ⁴ ; post 0.5,2,4,8,12 h)	X (24 h)	X (48 h)	X (72 h)

Study procedures	Screening visit ¹ (Day -14 to Day -2)	100 mg, 200 mg, 800 mg and 1200 mg groups				
		Day -1	Day 1	Day 2	Day 3	Day 4
Monitoring and recording of adverse events	X	X	X	X	X	X
PK sample collection ^{2,5}						
Blood samples			X (pre-15 min; post 0.5,1,2,3,4,6,8,10,12,16 h)	X (24,36 h)	X (48 h)	X (72 h)
Clinical study drug dispensing						
Drug administration			X			
Discharge from the study site						X

Abbreviations: pre = pre-dose; post = post-dose

1. Subject screening is performed within 14 days prior to the first dose (Day 1), with the same screening procedure for each group;
2. If multiple assessments are to be performed at the same time, samples/data should be collected in the following order in the non-emergency state: PK sample, 12-lead ECG, vital signs, followed by all other assessments. 12-lead ECG, blood pressure, and pulse should be measured after the subject has rested in supine position for approximately 5 min;
3. If clinical laboratory tests are performed within Day -2 at screening, the results could be used as baseline values and no additional tests are required.
4. The values of 12-lead ECG and vital signs measured before administration on Day 1 are taken as the baseline values;
5. Based on the results of the analysis of the pharmacokinetic data of the 100 mg group, fine adjustments may be made to the frequency and number of blood collections for the dose groups to be tested.

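### Do the unnamed ANOVA terms, the one-cycle subjects and the missing Day 5 pre-dose rule leave the food-effect conclusion open?

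*Combined protocol and SAP*

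**What the plan says.** The Synopsis (Methodology) randomizes the 400 mg group to two sequences, fasted then fed or fed then fasted. Each sequence has 8 subjects on TNP-2092 and 1 on placebo, treated "for two cycles, with a wash-out period of 4 days". Doses fall on Day 1 and Day 5.

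Under Food effect analysis, the plan invokes the bioequivalence principle. Food is taken to have no effect if the fed/fasted 90% confidence intervals for Cmax, AUC0-t and AUC0-∞ all lie within 80.00-125.00%. The model description is brief: AUC and Cmax "are subjected to variance analysis after log transformation". No terms are listed and no analysis set is named in that paragraph.

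Under Population for analyses, the Bioequivalence Set is defined specifically for the food effect. It requires no major violations and "no protocol deviations that had impact on PK endpoints", and it admits subjects "who must have received at least one cycle of treatment in the crossover study and have at least one evaluable pharmacokinetic parameter". The general PK paragraph says "Pharmacokinetic analysis will be based on the PKPS".

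The plasma schedule includes a sample at "Day 5: Before administration (within 15 minutes), and 0.5 h" and later times. Nothing says what is done if that pre-dose value is quantifiable. The one stated use of the 100 mg PK results is that "fine adjustments may be made to the frequency and number of blood collections for the dose groups to be tested" (Appendix 1, note 5; repeated in Appendix 2).

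**The concern.** An interval that decides an objective should come from a stated model. Read literally, a variance analysis on log values could be a treatment-only comparison, a fixed-subject crossover ANOVA or a mixed model. An analysis set that needs only one cycle is compatible with all three. If the subject term were left out, between-subject variability would enter the interval, and a drug with no food effect would often fail the criterion. One-cycle subjects would then also shift the mean of one condition but not the other.

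The second worry is residual drug. Cycle 2 starts 96 h after the first dose, and the documents give no half-life. Drug left over from cycle 1 raises cycle-2 exposure in both sequences and pulls a true ratio other than 1 toward 1. The sample that would reveal this is collected without a rule for using it.

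**Working it through.** **Inputs from the documents.** The head count reproduces: 4×10 + 18 = 58 subjects; active 4×8 + 2×8 = 48; placebo 4×2 + 2×1 = 10. The food-effect comparison therefore has 16 active subjects, 8 per sequence. The limits are 80.00-125.00% with 90% intervals, and doses are 96 h apart. There is no power or precision figure to reproduce.

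**Assumptions, because the documents give none.** Within-subject CV 20% (also 30% and 40%); between-subject CV 20-50%; half-life 12, 24 or 36 h; true ratio 1.00 or 1.25. The log-scale SD is s = √ln(1+CV²).

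**1. Effect of the model terms, 16 completers, observed ratio 1.00.**
- Crossover terms: half-width = t(0.95, 14) × s_w × √(2/16) = 1.761 × 0.198 × 0.354 = 0.123. The interval is 88.4-113.1%.
- Treatment only, between-subject CV 40%: t(0.95, 30) × √(0.148 + 0.039) × 0.354 = 1.697 × 0.433 × 0.354 = 0.260. The interval is 77.1-129.7%.

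Simulated chance of meeting the limits for one parameter at true ratio 1.00 and within-subject CV 20%:

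| Model | Between-subject CV | Meets limits |
|---|---|---|
| Crossover terms | any | 83% |
| Treatment only | 20% | 56% |
| Treatment only | 30% | 22% |
| Treatment only | 40% | 5% |
| Treatment only | 50% | 1% |

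The 83% depends on the assumed 20%. The crossover model itself gives about 33% at a within-subject CV of 30% and 7% at 40%.

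**2. Direction of the error.** At true ratio 1.25 and within-subject CV 20%, dropping the subject term lowers the false no-effect rate from about 5% to 1.2% (between-subject CV 20%) and to under 0.1% (40%). The error would be a failure to claim no effect, not a false claim of it.

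**3. One-cycle subjects under a crossover model.**
- Fixed subject effects: with three one-cycle subjects in one sequence, the estimate and interval equal those from completers alone (difference below 1e-15).
- Random subject effects: the completers-only standard error is √[(s_w²/2)(1/5 + 1/8)] = √(0.0196 × 0.325) = 0.0798. The mixed model with known variances (between-subject CV 40%) gives 0.0789, about 1% smaller. The fixed-or-random choice hardly matters.
- Period term: with those three subjects and an assumed period effect of 0.1 on the log scale, omitting the term moves the average ratio from 1.00 to 0.976. Including it, as the standard model does, leaves the ratio at about 1.00.

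**4. Residual drug.** With a mono-exponential decline, the fraction carried into cycle 2 is r = 2^(−96/t½): 0.4%, 6.3% and 15.8% at 12, 24 and 36 h. For a true ratio θ, the fasted-first sequence shows θ + r and the fed-first sequence shows θ/(1 + rθ). The estimate is the geometric mean, √[(θ + r)θ/(1 + rθ)].
- θ = 1: √[(1 + r)/(1 + r)] = 1, so there is no bias.
- θ = 1.25, 24 h: √(1.3125 × 1.25/1.0781) = 1.234. At 12 h and 36 h the result is 1.249 and 1.212.

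The plan requires all three parameters to pass. In a simulation of the scheduled sampling times at θ = 1.25 (one-compartment oral profile, within-subject CV 20%, between-subject CV 40%), the all-three pass rate is 3.6%, 4.8% and 6.8% at 12, 24 and 36 h, against about 3% with no residual drug.

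**The case for a change.** The best case for a change runs as follows. The plan explains its bioequivalence principle as a rule about limits, not as a model. Two analyses that both fit the words could return opposite verdicts on the same data. The trial may be exploratory, but the criterion is formal and its conclusion categorical. Stating the terms costs a sentence. Residual drug after a correctly performed wash-out is not a protocol deviation, so the exclusion clause of the Bioequivalence Set does not cover it. For a single parameter, the false pass rate already reaches about 7% at a 24 h half-life in a simple check.

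Some of this stands. The terms, the set for the interval and a pre-dose rule are indeed absent, and a fuller text would state them.

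It does not show a wrong plan. The treatment-only reading discards the pairing that the crossover was built to provide, in a paragraph that otherwise follows bioequivalence practice: log scale, geometric mean ratios, 90% intervals and the conventional limits. The set is labelled for the food effect, which settles where it applies despite the general sentence on the PKPS. One parameter alone cannot deliver the no-effect conclusion. Any pre-dose rule would be one of several defensible choices. Subtracting an extrapolated residual would serve only as a sensitivity analysis, leaving the primary ratio and decision as they are. At 36 h it also costs precision for AUC0-∞: the pass rate at true ratio 1.00 falls from 75% to 69%.

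**Conclusion.** No change follows. The model description is incomplete in a way that analysts fill in only one sensible manner: sequence, subject within sequence, period and treatment on the log scale. Under that model the one-cycle clause is harmless, and the fixed-or-random choice shifts the standard error by about 1% in the case checked. The large contrast (83% against 5% meeting the limits) belongs to a model that the plan does not prescribe. Even that model would err toward not claiming an absence of food effect.

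The residual-drug point is conditional on a half-life the documents do not give. It vanishes at a true ratio of 1. Of the half-lives tried, the false all-three pass rate exceeds 5% only at 36 h (6.8%). The Day 5 pre-dose sample is scheduled, so any residual will be visible when the results are read.

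These sizes rest on assumed CVs, half-lives and numbers of one-cycle subjects. The conclusion rests mainly on the stated crossover design and bioequivalence criterion, which do not depend on those assumptions.

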4. The values of 12-lead ECG and vital signs measured before administration on Day 1/Day 5 are taken as the baseline values in Cycle 1 and Cycle 2, respectively;
5. Based on the results of the analysis of the pharmacokinetic data of the 100 mg group, fine adjustments may be made to the frequency and number of blood collections for the dose groups to be tested;
6. Urine and stool samples are collected from subjects in Group A of the 400 mg group for the metabolic transformation study.

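### Does the mid-study review of 100 mg PK data contradict the no-interim-analysis statement, break the blind, or spoil the comparison across doses?

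*Combined protocol and SAP*

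**What the plan says.** The synopsis, under Statistical methods (Interim analysis), says "No interim analysis is planned". Footnote 5 of Appendix 1 says of the 100, 200, 800 and 1200 mg schedule: "Based on the results of the analysis of the pharmacokinetic data of the 100 mg group, fine adjustments may be made". What may change is given in the same sentence: "fine adjustments may be made to the frequency and number of blood collections for the dose groups to be tested". Footnote 5 of Appendix 2 repeats the allowance for the 400 mg food-effect group.

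The Methodology section describes a double-blind, placebo-controlled trial. The four groups other than 400 mg are set up "with 10 subjects randomized in each group, 8 subjects receiving TNP-2092 and 2 receiving placebo". Moving to the next dose depends on the safety and tolerability of the previous one; PK is not named as a criterion. The planned sampling times are the same in every group: pre-dose and 14 post-dose samples to 72 h, and in the 400 mg group the same grid on Day 1 and Day 5.

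The safety criteria include "the relationship between the drug and AEs". The PK criteria include AUC0-t, AUC0-inf and Cmax. Across doses, the PK analysis section plans only descriptive summaries and plots of dose-standardised parameters, inspected for trends.

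**The concern.** Three things look wrong on a first reading.

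- **Wording.** One section denies any interim analysis; two footnotes foresee an analysis of the first cohort that can change how later cohorts are sampled. The supplied text does not say who sees those data or how far an adjustment may go.
- **Blind.** Placebo subjects have no drug to measure, so individual concentrations show who received what. If they reached site staff, causality ratings of adverse events in that cohort could be coloured.
- **Comparability.** AUC0-t depends on the last sampling time, and observed Cmax on how densely the peak is sampled. If the grid changes after 100 mg, part of any difference between 100 mg and the higher doses could come from the schedule. With 8 active subjects per group (16 at 400 mg) and a visual assessment, such a shift might be read as a departure from dose proportionality.

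**Working it through.** **1. The plan's own numbers.** Total: 4 × 10 + 2 × 9 = 58. Active: 4 × 8 + 2 × 8 = 48. Placebo: 4 × 2 + 2 × 1 = 10. All three agree with the synopsis (Number of subjects).

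**2. Is there a statistical contradiction?** The synopsis says the sample size does not rest on a hypothesis test. It states no alpha, power, stopping boundary or interim decision on efficacy. The 100 mg review can alter only blood-collection times. If the term interim analysis is taken in its usual sense of a formal inferential look, the two statements are compatible, and the review is disclosed in advance in both schedules. Calling it an interim look would change no estimate, interval or error rate.

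**3. How far can the blind be affected?** With 8 active and 2 placebo there are C(10,2) = 45 possible allocations of the 100 mg group. Individual concentrations would in practice single out one. That exposes at most 10 of 58 subjects (17%) and says nothing about the other 48. As to timing, dosing is on Day 1, so the 72 h sample falls on Day 4. Appendix 1 places the last scheduled adverse-event monitoring and discharge on Day 4 as well, and the Methodology section sets the tolerability evaluation on that day. A review of the complete profile therefore comes after scheduled observation of that cohort.

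**4. How far can the PK parameters move?** The documents give no half-life or Tmax, so these are assumptions.

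Simple check, mono-exponential decline, 72 h sample dropped after 100 mg:

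AUC0-48 / AUC0-72 = (1 − 2^(−48/h)) / (1 − 2^(−72/h)), with h the half-life.

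- h = 24 h: 0.750 / 0.875 = 0.857, a fall of 14%.
- h = 12 h: 0.9375 / 0.9844 = 0.952, a fall of 5%.

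Fuller check: one-compartment oral curve, half-life 4 to 24 h, Tmax 1.5 to 4.5 h, linear trapezoid, no assay noise. Ratios are altered grid to planned 15-sample grid:

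| Change to the grid | Cmax | AUC0-t |
|---|---|---|
| Remove interior samples (3 h; 1 and 3 h; 10 and 16 h; or 36 h) | 0.961–1.000 | 0.984–1.041 |
| Add 1.5, 2.5 and 5 h | 1.000–1.028 | 1.000–1.003 |
| Stop at 48 h | 1.000 | 0.846–0.999 |
| Stop at 24 h | 1.000 | 0.547–0.977 |

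For the stop at 48 h, AUC0-inf stays at 0.992–1.000. So interior changes move either parameter by about 4% at most. Only a shorter sampling span matters, and then for AUC0-t alone.

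**5. Is a shorter span likely?** The footnote speaks of fine adjustments and makes them optional. Subjects are still on site at 72 h, with laboratory tests, ECG and vital signs due then, so dropping that blood sample would save little.

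**6. Does the food-effect comparison suffer?** The trigger is the 100 mg data, and the 400 mg group starts only after a favourable 200 mg evaluation. Any adjustment would be expected before either 400 mg cycle. The plan lists identical grids for both cycles, and the fed-to-fasted ratio is formed within that group.

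**The case for a change.** The strongest case for acting is that nothing in the supplied text limits the change. The word fine is undefined, the allowance covers the number as well as the frequency of collections, and no last sampling time or common core grid is protected. A drop from 72 h to 48 h would lower AUC0-t at every dose above 100 mg in the same direction, by up to 15% in the illustration. Nor does the text keep subject-level data from blinded staff. A paragraph would settle all of this.

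Part of this stands. The text does leave access and limits open, and a sentence would do no harm. But only a synopsis and schedules are supplied, so handling of blinded PK data may be described elsewhere. The 15% needs both a half-life near 24 h and removal of a sample the plan gives no reason to remove. Even then, one adjustment after 100 mg would separate that group from the rest; it would not create a gradient from 200 to 1200 mg. AUC0-inf is already reported and hardly moves, and an analyst facing unequal grids can compute AUC to a common time from the data collected. Forbidding removal of any listed sample would defeat part of the purpose of footnote 5, which is to let the first cohort inform later sampling.

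**Conclusion.** The wording is loose, but no rule in the plan gives a wrong result as written. The 100 mg review is a disclosed, non-inferential look; no error rate depends on it, and escalation does not use it. Possible unblinding is confined to at most 10 of 58 subjects, requires individual concentrations to reach blinded staff, and would follow that cohort's last scheduled adverse-event monitoring. What remains is late or revised causality ratings.

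For comparability, interior changes shift Cmax or AUC0-t by about 4% at most. A 48 h cut-off would lower AUC0-t by 0.1% to 15% while leaving Cmax unchanged and AUC0-inf within 1%. These figures rest on an assumed one-compartment model with half-lives of 4 to 24 h and Tmax of 1.5 to 4.5 h. The comparison they could affect is a descriptive plot with no test or decision attached. Access to the data and the size of an adjustment are operating details that a PK team would fill sensibly, and freedom to trim samples is a fair trade-off in a first cohort-by-cohort study. No change is called for.
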